## 1. PROTOCOL SUMMARY

**Title:** Meso BioMatrix Breast Reconstruction Feasibility Trial

**Investigational Device Description:** The Meso BioMatrix™ Acellular Peritoneum Matrix (“Meso BioMatrix) is a bioresorbable porcine mesothelium-derived surgical mesh intended for reinforcement of soft tissues. The device is supplied sterile in double-layer packages. Meso BioMatrix is replaced by host tissue during the healing process.

**Clinical Investigation Intended Use:** The Meso BioMatrix implant is intended for implantation to reinforce soft tissues where weakness exists in subjects requiring soft tissue repair and/or reinforcement during breast reconstruction surgery.

**Design:** Prospective, multi-center, single-arm, feasibility phase trial.

**Purpose:** Demonstrate the feasibility and initial safety of the Meso BioMatrix for the reinforcement of weak soft tissue during two-stage, tissue expander-assisted breast reconstruction.

**Primary Hypothesis:** Meso BioMatrix can be safely used to provide reinforcement for the weak inferior mastectomy skin flaps during two-stage, tissue expander-assisted breast reconstruction.

**Enrollment:** A total of 25 subjects.

**Clinical Sites:** 10 clinical sites in the United States will participate.

**Subject Population:** Subjects undergoing two-stage, tissue expander-assisted breast reconstruction meeting eligibility criteria.

**Follow-up Visits:**

- Office visits at 1 week and 2 weeks after Meso BioMatrix implantation followed by every 1 – 4 weeks for tissue expansion.
- Office visits at 1 week, 1 month, 3 months, 6 months and 12 months after the tissue expander is exchanged for a permanent breast implant.

**Primary Endpoint:** Rate of breast related adverse events throughout the follow-up period.

**Secondary Endpoints:**

- Rate of all serious adverse events throughout the follow-up period.
- Presence of host tissue integration into the Meso BioMatrix mesh at the time of tissue expander / implant exchange.
- Breast-Q™ Satisfaction with Breast score at the last follow-up visit.

## 2. TRIAL TITLE

Meso BioMatrix Breast Reconstruction Feasibility Trial

## 3. INVESTIGATIONAL DEVICE

### 3.1. Meso BioMatrix™ Implant

The device under investigation is the Meso BioMatrix™ Acellular Peritoneum Matrix (“Meso BioMatrix”)

### 3.2. Regulatory History of Device

The United States Food & Drug Administration (“FDA”) cleared Meso BioMatrix for marketing via the 510(k) clearance pathway in May 2010 (K094061).

### 3.3. 510(k) Cleared Indication

Meso BioMatrix™ is intended for implantation to reinforce soft tissues where weakness exists in subjects requiring soft tissue repair, reinforcement in plastic and reconstructive surgery, and in the urological, gynecological, and gastroenterological anatomy including but not limited to the following procedures: reinforcement of primary closure such as suture line reinforcement and muscle flap reinforcement; hernia repair (e.g., hiatal, femoral, paracolostomy, umbilical), urethral and vaginal prolapse repair, colon and rectal prolapse repair, reconstruction of the pelvic floor, bladder support, and sacrocolposuspension.

### 3.4. Clinical Investigation Intended Use

The Meso BioMatrix™ implant is intended for implantation to reinforce soft tissues where weakness exists in subjects requiring soft tissue repair and/or reinforcement during breast reconstruction surgery.

### 3.5. Description of Device

The Meso BioMatrix™ implant is a resorbable surgical mesh intended to reinforce soft tissue where weakness exists. The implant is derived from porcine peritoneum and is supplied sterile in double layer packages. The implant is packaged dry and prior to use is hydrated with saline or autologous body fluids such as blood, bone marrow aspirate, or blood concentrates such as platelet rich plasma. Meso BioMatrix provides structural and mechanical support to weak soft tissue during the healing process. Meso BioMatrix is fully replaced with native tissue between 6 and 12 months.

## 4. BACKGROUND INFORMATION

### 4.1. Two-stage, Tissue Expander Assisted Breast Reconstruction

Following mastectomy, women may elect to have breast reconstruction with autologous tissue or breast implants. Two-stage, tissue expander assisted breast reconstruction is one of the common surgical methods that could be selected to reconstruct the breast. This method either begins immediately after the general surgeon completes the mastectomy (immediate breast reconstruction) or at some time afterward (delayed breast reconstruction). During the first stage of the breast reconstruction procedure, the plastic surgeon releases the pectoralis muscle from the chest wall in order to create a pocket for the prosthesis. Then, a tissue expander is implanted beneath the pectoralis muscle and partially inflated. The tissue expander is gradually filled with saline over several weeks or months. Once the desired breast volume has been achieved, the second stage of the reconstruction takes place. In the second stage, the tissue expander is removed and replaced with a permanent saline or silicone gel breast implant. Historically, surgeons placed the tissue expander and breast implant either completely or partially under the pectoralis muscle. However, these methods of breast reconstruction have been associated with

less favorable aesthetic outcomes. Therefore, in the early 2000s, surgeons started using AlloDerm® Regenerative Tissue Matrix (LifeCell Corporation, Branchburg, NJ), an acellular dermal matrix derived from human cadaveric tissue, to reinforce the inferior mastectomy skin flap and attempt to improve aesthetic outcomes. Use of AlloDerm to reinforce the inferior mastectomy skin flap gives surgeons better control of the lower pole of the breast during reconstruction and has been associated with less pain, fewer tissue expansions and improved aesthetic outcomes. However, AlloDerm adds significant cost to the procedure and some surgeons have seen an increased rate of post-operative complications such as infection, seroma, and hematoma when using AlloDerm, while others have seen no significant difference in the rate of complications with and without AlloDerm in tissue expander-assisted breast reconstruction. It has been suggested that these increased risks may be related to the surgical technique learning curve, foreign body reaction or the fact that AlloDerm is considered aseptic but not sterile.

AlloDerm is regulated by the FDA according to the U.S. Code of Federal Regulations, Title 21, Part 1270 - Human Tissue Intended for Transplantation and Part 1271 - Human Cells, Tissues, and Cellular and Tissue-based Products. AlloDerm is indicated for repair or replacement of damaged or inadequate integumental tissue or for other homologous uses of human integument. Therefore, use of AlloDerm in breast reconstruction could be considered an off-label use. At present, there are no biologic surgical mesh devices approved or cleared by the FDA for use in breast reconstruction.

#### 4.2.

#### Relevant Systematic Literature Reviews

Three recent systematic literature review articles were published regarding the use of acellular dermal matrices (“ADM”) during breast reconstruction. Jansen et al. tabulated adverse events from 14 relevant articles presenting outcomes after use of AlloDerm^16. Newman et al. tabulated adverse events from 12 relevant articles reporting outcomes after use of AlloDerm. It should be noted that 3 of those 12 articles included 3 other biologic mesh devices along with AlloDerm^17. Hoppe et al. tabulated adverse events from 7 relevant articles comparing outcomes with and without the use of AlloDerm during breast reconstruction. The adverse events tabulated in their systematic reviews are compared in Table 1.

Table 1: Adverse Events Listed Systematic Review Articles for Breast Reconstruction

Adverse Event Term	Jansen et al.* (AlloDerm only)	Newman et al. (ADM)	Hoppe et al. (AlloDerm only)
Breast Reconstruction	# of Implants = 655	# of Implants = 789	# of Implants = 977
Infection	0 - 11%	5.2%	7.6%
Seroma	0 - 9%	6.0%	9.4%
Necrosis	0 - 25%	9.4%	Not reported
Hematoma	0 - 6.7%	Not reported	1.4%
Exposure w/ Prosthesis Loss	0 - 14%	Not reported	Not reported
Exposure w/ Prosthesis Salvage	0 - 4%	Not reported	Not reported
Capsular Contracture	0 - 8%	Not reported	Not reported

\* Only probability ranges were presented due to limitations in underlying data

Jansen et al. and Hoppe et al. compared the rates of AlloDerm associated adverse events to adverse events in breast reconstruction without a biologic mesh. Jansen et al. found comparable rates of adverse events when a biologic mesh is used for breast surgery versus no biologic mesh use. However, Hoppe et al. found higher rates of adverse events when AlloDerm is used, but concluded that AlloDerm use may lead to greater patient satisfaction. It is important to note that the majority of articles in the above systematic review articles were retrospective, single-center

experiences. Such articles are prone to bias since adverse events are usually not uniformly defined and documented. Therefore, the true incidence of complications may have been underreported in the studies included in the above systematic reviews.

The potential benefits to AlloDerm assisted breast reconstruction cited in these systematic review articles are:

- Increased initial tissue expander fill volume
- Reduced operative time
- Reduced time to full expansion
- Reduced time from tissue expander to breast implant exchange
- Reduced post-operative and tissue expansion pain
- Improved aesthetic outcome
- Less capsular contracture

The aforementioned authors all concluded that the potential benefits, when balanced with the potential complications, warrant additional study of the use of biologic surgical mesh for breast reconstruction.

#### **4.3. Preclinical Testing**

In-vitro bench tests and in-vivo animal studies have been performed to assess the safety and effectiveness of Meso BioMatrix for soft tissue repair and reinforcement. The pre-clinical testing demonstrated that the device is biocompatible and is replaced by native tissue during the healing process. A summary of the pre-clinical testing can be found in the Report of Prior Investigations in the Investigational Device Exemption (“IDE”) application. The Report of Prior Investigations will be provided separately to the investigational sites along with the Investigational Plan.

#### **4.4. Justification for the Trial**

There exists a clinical need for a bioresorbable surgical mesh to support the lower pole of the breast during breast reconstruction. The ideal bioresorbable surgical mesh should be associated with a low rate of complications and a high rate of aesthetic success, while being cost effective to the subject and healthcare system. DSM Biomedical has developed a sterile bioresorbable surgical mesh with mechanical and handling properties similar to AlloDerm. This product may provide similar benefits as those associated with the use of AlloDerm during breast reconstruction and may reduce the risk of post-operative complications associated with AlloDerm. Therefore, a well-designed feasibility trial is warranted to evaluate the feasibility and initial safety of the use of Meso BioMatrix during breast reconstruction.

### **5. TRIAL INTRODUCTION**

#### **5.1. Trial Design**

The trial is designed as a prospective, multi-center, single-arm, feasibility phase trial of subjects undergoing two-stage, tissue expander-assisted breast reconstruction.

#### **5.2. Primary Trial Hypothesis**

Meso BioMatrix can be safely used to provide reinforcement for the weak inferior mastectomy skin flaps during two-stage, tissue expander-assisted breast reconstruction.

#### **5.3. Purpose**

The purpose of the trial is to demonstrate the feasibility and initial safety of the Meso BioMatrix for the reinforcement of weak soft tissue during two-stage, tissue expander-assisted breast reconstruction.

**5.4. Trial Objectives**

The primary objective of this trial is to demonstrate the feasibility and initial safety of the Meso BioMatrix when use during breast reconstruction. If successful, the data collected in the feasibility phase trial may be used to support an IDE supplement for a pivotal phase trial.

**5.5. Primary Endpoint**

The primary endpoint of this feasibility phase trial is the rate of post-operative breast related adverse events through 12 months after the second stage of the breast reconstruction.

**5.5.1. Primary Endpoint Justification**

The primary endpoint of breast related adverse events provides an objective means to assess the initial safety of the Meso BioMatrix implant when used during breast reconstruction.

**5.6. Secondary Endpoints**

The secondary endpoints that will be evaluated in this trial are:

- Rate of all serious adverse events after Meso BioMatrix implantation through 12 months after the second stage of the reconstruction;
- Presence of host tissue integration into the Meso BioMatrix mesh at the time of second stage of the breast reconstruction;
- Breast-Q Satisfaction with Breast score at the final post-operative trial visit.

**5.7. Follow-Up Duration**

Subjects enrolled in this trial will have trial required follow-up visits through 12 months after the second stage of the breast reconstruction. It is estimated that the second stage of the reconstruction will occur between 3 to 6 months after the first stage. Therefore, each subject will be followed for approximately 15 to 18 months after Meso BioMatrix implantation, which is approximately two times the duration of Meso BioMatrix bioresorption. The follow-up visits are to occur according to the follow-up schedule described in Section 7.6 of this protocol.

**5.8. Endpoint Evaluation Criteria**

**5.8.1. Primary Endpoint Evaluation**

At each operative and post-operative visit, Investigators will document the presence or absence of breast related adverse events occurring since the prior visit. All breast related adverse events documented during trial-required visits will be recorded on the trial case report form. When one or more breast related adverse events are reported at one or more of the follow-up visits for an individual subject, the occurrence of the primary endpoint will be documented for that subject.

**5.8.2. Secondary Endpoint Determination**

The occurrence of each of the secondary endpoints will be determined as follows:

- At each visit, starting with the Meso BioMatrix implantation visit, Investigators will document the presence or absence of serious adverse events. All serious adverse events will be recorded on the trial case report form. When a serious adverse event is recorded at one or more follow-up visits for an individual subject, the occurrence of this secondary endpoint will be documented for the subject.
- During the second stage of the breast reconstruction, the tissue expander is surgically removed and replaced with a permanent breast implant. This second surgery provides the Investigator with an opportunity to visually inspect the condition Meso BioMatrix implant and take biopsies to assess the type and degree of host tissue integration within the implant. The biopsies taken during the second stage of the reconstruction will be preserved and sent to a central core laboratory for standardized analysis. If host tissue is found within an individual subject's biopsy specimen, than the occurrence of this secondary endpoint will be documented for the subject.

- At the 6 and 12-month visits after the second stage of the breast reconstruction, subjects will complete the Breast-Q Satisfaction with Breast survey. Each Breast-Q survey will be scored according to the author's instructions. Descriptive statistics will be presented for the Breast-Q Satisfaction with Breast scores at 6 and 12 month after the second stage of the reconstruction.

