### 7.6. **Schedule of Trial Required Visits and Visit Requirements**

The required visits and the trial requirements at each visit are listed in Table 2 below.

Table 2: Schedule of Required Visits and Visit Requirements:

Required Visits	Visit Requirements
Pre-operative (Within 60 days pre-operative)	1. Medical History 2. Inclusion – Exclusion Criteria Screening 3. Photographs 4. Informed Consent
1 st Stage of Reconstruction: Tissue Expander and Meso BioMatrix Implantation	1. Skin flap viability assessment 2. Adverse Event Assessment 3. Photographs, only if breast adverse event 4. Patient Diary given at discharge
1 Week Post 1 st Stage Surgery (5 – 12 days)	1. Adverse Event Assessment 2. Photographs, only if breast adverse event
2 Weeks Post 1 st Stage Surgery (12 – 21 days, not to be combined with 1 st post-op visit)	1. Adverse Event Assessment 2. Photographs, only if breast adverse event 3. Collect patient diary
Tissue Expansion Visits (start after incision healing, then every 1 -4 weeks as tolerated until full expansion)	1. Tissue Expansion 2. Adverse Event Assessment 3. Photographs, only if breast adverse event
2 nd Stage of Reconstruction: Tissue Expander – Implant Exchange (expected between 2 - 6 months after 1 st stage)	1. Meso BioMatrix Biopsies 2. Adverse Event Assessment 3. Photographs, only if breast adverse event
1 Week Post 2 nd Stage Surgery (5 – 14 days)	1. Adverse Event Assessment 2. Photographs, only if breast adverse event
1 Month Post 2 nd Stage Surgery (23- 44 days)	1. Adverse Event Assessment 2. Photographs, only if breast adverse event
3 Months Post 2 nd Stage Surgery (2 – 4 months)	1. Adverse Event Assessment 2. Photographs, only if breast adverse event
6 Months Post 2 nd Stage Surgery (5 – 7 months)	1. Adverse Event Assessment 2. Photographs, only if breast adverse event 3. Breast-Q

Required Visits	Visit Requirements
12 Months Post 2 nd Stage Surgery (11 – 13 months)	1. Adverse Event Assessment 2. Photographs 3. Breast-Q

Note, with the exception of obtaining biopsy specimens during the second stage of the reconstruction, all evaluations, procedures and follow-up visits for this trial are part of the standard of care for patients undergoing two-stage, tissue expander-assisted breast reconstruction.

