### **11.2. Statistical Analysis**

#### *11.2.1. Data Presentation*

All clinically relevant demographic, baseline, procedure and outcome variables will be summarized by scheduled visit using frequency tables and descriptive statistics as appropriate in accordance with sections 8.2, 8.3, 8.4, 8.7 and 8.8 of the Guidance for Industry and FDA Staff – Saline, Silicone Gel and Alternative Breast Implants.

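### The host tissue integration endpoint keeps only a yes/no from a biopsy whose timing is neither fixed nor used in the summary, so it cannot show the extent of ingrowth or relate it to time since implantation

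*Combined protocol and SAP*

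**What the plan says.** Section 5.6 lists the endpoint as "Presence of host tissue integration into the Meso BioMatrix mesh at the time of second stage of the breast reconstruction". Section 5.8.2 gives the purpose of the second-stage biopsies as to "take biopsies to assess the type and degree of host tissue integration within the implant" and sends them to a core laboratory for standardized reading. The operative rule in the same paragraph is binary: "If host tissue is found within an individual subject's biopsy specimen", the endpoint counts as met for that subject.

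Section 7.5.2 lists four specimens. Three come from the mesh (the pectoralis interface, the centre and the inframammary fold interface). The fourth comes from the capsule behind the expander and is labelled a control. The note in section 7.3.3 says the second-stage steps are repeated in the other breast of a bilateral subject.

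On timing, section 7.3.3 plans the exchange once the expander is sufficiently filled. Table 2 (section 7.6) says it is "expected between 2 - 6 months after" the first stage. Section 5.7 says: "It is estimated that the second stage of the reconstruction will occur between 3 to 6 months after the first stage". Section 3.5 states that "Meso BioMatrix is fully replaced with native tissue between 6 and 12 months", and section 4.3 reports from preclinical work that the device "is replaced by native tissue during the healing process".

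On analysis, section 11.2.1 says outcome variables "will be summarized by scheduled visit using frequency tables and descriptive statistics". Section 11.1 states that there is no formal hypothesis and that 25 subjects were chosen empirically. The success criteria in section 11.4.2 concern adverse events only.

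**The concern.** The biopsies are taken to learn how far host tissue has grown into the mesh, but the endpoint discards that information. A specimen with a trace of ingrowth and one with advanced ingrowth both score yes. Because replacement is a process in time, the state expected at biopsy depends on how long the mesh has been in place. That interval varies between subjects and has no place in the planned summary.

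These biopsies are the only planned tissue-level check in subjects that the mesh behaves in the breast as it did in preclinical testing. According to the note under Table 2, they are also the one study procedure outside standard of care, and section 9.5 lists risks attached to them. A summary that can take a high value without saying how far integration has progressed is a poor return on that procedure, and a weak basis for any statement about integration if the data support a pivotal trial.

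**Working it through.** The plan gives no figure to reproduce: no expected integration rate, threshold, alpha or power. The check therefore compares the stated purpose with the scoring rule and then uses illustrative arithmetic on labelled assumptions.

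**1. Purpose against rule.** The purpose in section 5.8.2 is graded and the rule is binary. The protocol text available for review contains no grade, no minimum amount of tissue, no residual-mesh category and no planned summary of extent. Section 7.5.2 describes the separate core laboratory manual as covering collection, preservation and shipping, not scoring.

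**2. Which specimens count.** A unilateral subject has 3 mesh specimens and 1 control. If all four are repeated in the second breast, as the note in 7.3.3 implies, a bilateral subject has 6 mesh specimens and 2 controls. The rule speaks of the subject's specimen in the singular, does not exclude the control, and does not say whether one positive site is enough. The wording of section 5.6 shows that integration into the mesh is meant. Read literally, however, host tissue in the capsule specimen alone would satisfy 5.8.2.

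**3. How high the yes rate could be.** Assume that any positive mesh specimen makes the subject positive, that the control is excluded, and that specimens are independent with per-specimen probability p. Then P(yes) = 1 − (1 − p)^k, with k = 3 (unilateral) or k = 6 (bilateral).

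| Assumed p | k = 3 | k = 6 |
|---|---|---|
| 0.3 | 1 − 0.7³ = 65.7% | 1 − 0.7⁶ = 88.2% |
| 0.5 | 1 − 0.5³ = 87.5% | 1 − 0.5⁶ = 98.4% |
| 0.7 | 1 − 0.3³ = 97.3% | 1 − 0.3⁶ = 99.9% |

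A 95% subject rate needs p = 1 − 0.05^(1/3) = 0.63 with three specimens, or 1 − 0.05^(1/6) = 0.39 with six. Positive correlation between sites would pull these subject rates down towards p. At the same p, a bilateral subject is more likely to score yes simply because more specimens are taken, so the mix of unilateral and bilateral subjects also moves the rate.

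**4. What a high rate would say.** If all 25 subjects scored yes, the exact 95% interval would be 0.025^(1/25) = 86.3% to 100%. That bounds the proportion with any host tissue found. It says nothing about extent.

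**5. Spread in time.** Divide the expected biopsy month by the stated month of full replacement, as a crude linear index:

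- earliest biopsy, slowest replacement: 2/12 = 0.17 (3/12 = 0.25 on the section 5.7 range)
- latest biopsy, fastest replacement: 6/6 = 1.00
- elapsed time alone: 6/2 = 3-fold on the Table 2 range, 6/3 = 2-fold on the section 5.7 range

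Table 2 gives each fixed post-operative follow-up visit a window, for example 11 to 13 months for the 12-month visit. The exchange has only an expectation. A summary by scheduled visit puts all these biopsies under one heading.

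**The case against.** The strongest reply has four parts.

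*No rate is stated.* A reader might infer that the endpoint is bound to come out near 100%. The documents do not support that. Section 4.3 gives no rate, no time point and no breast data, and the table above shows 66% to 88% of unilateral subjects positive at p of 0.3 to 0.5. Even a true subject rate of 95% would not guarantee 24 or 25 of 25: 0.95²⁵ + 25 × 0.05 × 0.95²⁴ = 0.277 + 0.365 = 0.64, leaving about a 36% chance of 23 or fewer. This part stands. Only 'likely to be high' is defensible.

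*Full replacement is mostly out of range.* A reader might say that the endpoint confuses slow ingrowth with complete replacement. On the protocol's own figures, biopsy at 2 to 6 months meets the 6 to 12 month completion range only at its edge, so complete replacement would be expected in few subjects. This also stands. The contrast that is lost is early against advanced partial ingrowth.

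*The data may still hold the answer.* A reader might infer that the trial itself cannot measure extent. The laboratory reads are meant to capture it, both surgeries are trial visits so the interval should be derivable, and section 11.2.1 does not forbid a tabulation by elapsed time. It also refers to sections of an FDA guidance not available here, and the core laboratory section listed in the contents is not in the reviewed text. The limitation therefore belongs to the endpoint as defined. What remains is that the available text commits no one to a graded read-out or to its analysis.

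*Nothing hangs on it.* The endpoint is secondary and descriptive, in a feasibility trial of 25 subjects, and is absent from section 11.4.2. That limits the weight of the point but does not answer it.

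**Conclusion.** The point holds in a limited form. Followed as written, the endpoint cannot distinguish early from advanced partial ingrowth or relate integration to time since implantation, and its scoring rule leaves open which specimens count and how sites and breasts combine. These conclusions rest on the protocol's wording alone.

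That the rate is likely to be high is a judgement. It depends on an any-positive reading, independence between sites and an assumed per-specimen probability; the range shown for unilateral subjects is about 66% to 97%. The documents support neither a forecast of near-certain saturation nor a claim that the underlying laboratory data are uninformative.

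The consequence is modest, because no hypothesis, threshold or progression criterion uses this endpoint. The change is worth making because it is cheap and recovers the information the biopsies are meant to provide.

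**What to change.** Make these changes before the laboratory read-out, so that categories are not chosen after results are seen.

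- **Sections 5.6 and 5.8.2:** define the endpoint as the core laboratory's graded degree of integration, together with residual-mesh status (for example present, partial or none identifiable), at each of the three mesh sites. Report the posterior control separately and exclude it from the endpoint. State how sites combine within a breast and how breasts combine within a subject.
- **Section 11.2.1:** present the graded result against months from Meso BioMatrix implantation to biopsy, for example as a scatter plot or subject listing. With 25 subjects, fixed time bands would be thin and are not needed. Keep the yes/no rate, from mesh sites only, as a supporting line.
- **Section 5.7 and Table 2:** reconcile the 3 to 6 month and 2 to 6 month statements. This review takes no position on which is right, and nothing here asks for the timing of surgery to change.

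The cost is wording in the protocol and analysis section and possibly in the laboratory form, which was not available for review. The biopsies, laboratory and surgery dates are those already planned. The downside is a slightly longer laboratory read-out and a result that is a distribution instead of a single percentage.
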